### 15.1.2 Maximum Accrual

Maximum accrual is 83 patients, which includes 10% over accrual to replace those patients deemed ineligible due to improper histology having been determined on the basis of information available prior to randomization.

### 15.1.3 Study Duration

Assuming a rate of 4 patients per month, the anticipated duration of accrual 21 months, (1.7 years). Assuming 12 months of follow-up (with tests required for disease assessment, per the Study Calendar) for every patient to assess the primary endpoint will bring maximum duration to 33 months (2.7 years) after the study opens to accrual, at which time all patients will be evaluable to assess the primary endpoint. This estimate may be adjusted if the study requires suspension for endpoint or toxicity concerns. All patients will be followed for a maximum of 3 years to capture data regarding survival, progression, and late occurring events.

### 15.1.4 Results Reporting on ClinicalTrials.gov

At study activation, this study will have been registered within the “ClinicalTrials.gov” web site. The Primary and Secondary Endpoints (ie, “Outcome Measures”) along with other required information for this study will be reported on ClinicalTrials.gov. For purposes of timing of the Results Reporting and as of Update #05, the initial estimated completion date for the Primary Endpoint of this study is 3 years after the study closes to accrual. The definition of “Primary Endpoint Completion Date” (PECD) for this study is the time the last patient registered has been followed for at least 12 months, but may be as high as 3 years, depending on the rate at which the events for the primary endpoint occur and given that the analysis is “event” (vs “time”) driven (per 15.1.1).

We note that the PECD may be further adjusted if the study requires suspension for toxicity concerns or re-design due to the planned interim look at the median PFS rate observed in the control arm.

### 15.1.5 Accrual Monitoring

We will be actively seeking participation from at least one of the other entities in the newly formed National Cancer Trials Network (formerly Cooperative Groups). We will follow the CTEP guidelines for monitoring accrual ([http://ctep.cancer.gov/protocolDevelopment/docs/slow\\_accrual.pdf](http://ctep.cancer.gov/protocolDevelopment/docs/slow_accrual.pdf)) for phase III studies. These rules are associated with accrual rates observed at the 5th, 6th, and 8th quarters following activation.

### 15.1.6 Evaluability & Assessment of Patients

We will perform an intent-to-treat analysis to assess the primary endpoint and all eligible patients will be included in the futility and efficacy analysis for progression-free survival, excluding patients deemed ineligible due to improper histology having been determined on the basis of information available prior to randomization. Given that the central-review of scans and pathology reports will be completed at a later date, we will consider the local review as the factor determining eligibility and evaluability for the progression-free survival endpoint. We will consider performing a secondary analysis, without such cases identified as discordant from the local review and to assess the impact of such cases on the results of the primary endpoint.

Patients on treated on the control/placebo arm are allowed to crossover to the sorafenib upon experiencing progressive disease. We will consider censoring disease assessments at the date of surgical or radiotherapy intervention in patients receiving such care, given that the patients are receiving non-protocol specified therapy (i.e. intervention) which may impact endpoint(s) beyond the treatment effect we are seeking to evaluate.

Patients who were receiving placebo and unblinded prior to progression, effective November 17, 2017, and crossing over to sorafenib, will be censored for the primary endpoint and at their most recent disease assessment prior to initiating crossover treatment.

## 15.2 Secondary Endpoints

NOTE: All secondary analyses and endpoints (except survival data/analyses) will exclude/censor data for patients (as applicable) receiving crossover treatment, due to the unblinding of study treatment effective November 17, 2017. The summary of data collected during crossover will further separate such patients from those who crossed over upon PD occurring during initial blinded treatment.

### 15.2.1 Adverse Events

We will use NCI CTCAE v4.0 to assess toxicity. Frequency tables, summary statistics, and categorical analysis will be used to compare the distributions of toxicity for patients treated with sorafenib vs placebo. Data for patients who have crossed over or having received surgical or radiotherapy intervention will be summarized independently from their primary course of study treatment.

#### **Data & Safety Monitoring**

The principle investigator(s) and the study statistician will review the study at least twice a year to identify accrual, adverse event, and any endpoint problems that might be developing. The Alliance Safety Monitoring Board (DSMB) is responsible for reviewing accrual and safety data for this trial at least twice a year, based on reports provided by the Alliance Statistics and Data Center.

### **Adverse Event Stopping Rules**

The stopping rules specified below are based on the knowledge available at study development. We note that the Adverse Event Stopping Rule may be adjusted in the event of either (1) the study re-opening to accrual or (2) at any time during the conduct of the trial and in consideration of newly acquired information regarding the adverse event profile of the treatment(s) under investigation. The study team may choose to suspend accrual because of unexpected adverse event profiles that have not crossed the specified rule below.

Accrual will be temporarily suspended to this study if at any time we observe events considered at least possibly related to study treatment (i.e. an adverse event with attribute specified as “possible”, “probable”, or “definite”) that satisfy either of the following:

- an excessive death rate, defined as 1% or higher mortality attributed to study drug, or
- if 3 or more patients in the first 15 treated patients experience a grade 3 or higher adverse event.
- We note that we will review grade 4 and 5 adverse events deemed “unrelated” or “unlikely to be related”, to verify their attribution and to monitor the emergence of a previously unrecognized treatment-related adverse event.

#### **15.2.2 Surgical Intervention**

Surgical excision/amputation is a therapeutic and palliative options for managing this disease. Time to surgical intervention during treatment is defined as time between randomization to the patient undergoing therapeutic surgical resection for this disease. If no event exists, patients will be censored at their date of last treatment for this event. A log rank test will be used to compare the distributions of time to surgical intervention between the two arms using a 2-sided test and  $\alpha=0.05$  level of significance. Kaplan-Meier (1958) methodology will be used to estimate various time points (e.g. 1 year rate, 2 year rate, etc.) and 95% Confidence Intervals will be calculated for these estimates. Surgery will be classified by outcome (e.g. complete-macroscopic, complete-microscopic, or partial), type, location (e.g. limb), thereafter analyzed by categorical analysis and descriptive statistics. Non-parametric methods will be used, as appropriate. See the note at the beginning of [Section 15.2](#).

#### **15.2.3 Overall Survival (OS)**

Survival will be calculated as the time between the date of randomization to until death. Patients who are alive at the time of the analysis will be censored for survival at the most recent date of the last contact (or lost to follow-up). Kaplan-Meier (1958) methodology and log rank tests will be used to compare OS between the groups at various time points (eg, 1 year rate, 2 year rate, etc) and 95% Confidence Intervals will be calculated for these estimates. Data following crossover will be analyzed and summarized separately from the main course of treatment for these patients. See the note at the beginning of [Section 15.2](#).

#### **15.2.4 Tumor Response**

Patients will be classified for disease status according to RECIST v1.1 (see [Section 13.0](#)). We will compare best objective status for the two treatment arms and using the Cochran-Mantel-Haenszel test. Duration of response will be calculated as the time between first tumor response and progression. Patients will be censored for duration of response at the date of last assessment if they have reached maximum follow-up without PD (or are lost to follow-up without PD). Kaplan Meier methodology will be used to estimate the distribution of duration of response and the Log-Rank test will be used to test for a difference in duration of response between the two arms. See the note at the beginning of [Section 15.2](#).

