### 1.2 Epidemiology and Clinical Presentation

DT/DF have an annual incidence of ~1000 in the United States, exhibiting a slight female preponderance and a wide age distribution (15-60 years). DT/DF have a wide range of presentation and have a variable natural history. DT/DF typically exhibit indolent growth, and if asymptomatic may be observed as primary management. In a subset of patients, DT/DF can have a waxing and waning pattern and on rare occasions exhibit spontaneous remission. However, DT/DF can cause significant deformity, loss of function, pain through mass effects requiring narcotics and poor quality of life. Mortality from DT/DF is low and is secondary to compromising vital structures in the abdominal cavity and retroperitoneum resulting in hydronephrosis and/or bowel/bladder obstruction or perforation. Given the low mortality, the prevalence of DT/DF is expected to be much higher.

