We will also be evaluating diffusion-weighted MR imaging (DW-MRI) in a subset of patients having extra-abdominal disease. DW-MRI is a non-invasive technique that derives its image contrast from differences in the motion of water molecules between tissues. The degree of water diffusion in biologic tissue is inversely correlated to tissue cellularity and the integrity of cell membranes. The motion of water molecules is more restricted in tissues with high cellular density associated with numerous intact cell membranes (e.g., tumor tissue). Quantitative analysis of DW-MRI is achieved by calculation of the apparent diffusion coefficient (ADC). The ADC is calculated for each pixel of the image and is displayed as a parametric map.

RECIST 1.1: Twenty four of 26 patients were evaluable for response. CT or MRI was obtained at a median interval of 4 months. Responses by RECIST 1.1 were: 0/24 complete responses, 6/24 partial responses (25%), 17/24 (70%) with stable disease and 1 patient with progressive disease. Seven patients experienced minor response (defined as 10–29% decrease). Bi-dimensional WHO size measurements were highly correlated ( $R^2=0.92$ ) with RECIST (not shown). RECIST PR was achieved at a median of 10 months and a minor response (i.e. reduction > 10% by RECIST) was noted at a median of 4 months of starting therapy. PR and SD were mostly seen in extra-abdominal tumors ( $p=0.03$ , t-test) and there was no difference between those who received sorafenib as first-line or second-line ( $p = 0.9$ , t-test).

**Survival:** The 26 patients were followed for a median of 50 months (3–209 months) from initial diagnosis. Median follow-up from the start of sorafenib was 12 months (1-46+). Median time to progression was not reached. Five patients progressed despite sorafenib, defined as increasing tumor size (2), symptoms (1) or drug intolerance (2). Twenty-five of 26 patients are alive with disease.

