**Decision Rule:** We will randomize a total of 75 patients (25-placebo, 50-sorafenib) and observe patients until we have reached 52 PFS events for the efficacy analysis. In the event the median PFS in the control group is larger than expected and long-term follow-up becomes a concern, we will perform the final efficacy analysis after 52 events are observed or after all evaluable patients have been followed for at least 3 years, whichever occurs earlier. If the 1-sided p-value associated with the Log-Rank test is  $< 0.0255$  (corresponding to an observed HR of 0.5776), we will consider sorafenib as having shown promising activity in this population and may recommend it for further testing.

**Inefficacy/Futility Analysis:** We will evaluate the observed PFS of the arms when 45% of the PFS events required for the final efficacy analysis (i.e., 24) have been observed.

We will terminate the study for futility if the p-value associated with the test statistic from a Log-Rank is at least 0.5025 (corresponding to an observed HR of 1.0027). Otherwise, we will continue to complete full enrollment.

Although the primary endpoint will be evaluated using the first 75 evaluable patients, final efficacy results will further report results (e.g., publication, presentation) using all patients evaluable for determining PFS and so that patient enrolled beyond these 75 may contribute to these estimates.

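### Duration of response is tested between arms in responders only, so the p-value is not a randomised comparison, its bias has unknown direction, and the test has very little power

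*Combined protocol and SAP*

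**What the plan says.** Section 15.2.4 (Tumor Response) plans two separate analyses. For response itself, "We will compare best objective status for the two treatment arms and using the Cochran-Mantel-Haenszel test". For duration, "Duration of response will be calculated as the time between first tumor response and progression". On patients without progression it says that "Patients will be censored for duration of response at the date of last assessment". It then plans a Kaplan-Meier estimate and adds that "the Log-Rank test will be used to test for a difference in duration of response between the two arms". No significance level, sidedness or power is given for that test. Non-responders receive no value, and nothing labels the comparison as descriptive or conditional on response.

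The note that opens Section 15.2 also governs this endpoint: "All secondary analyses and endpoints (except survival data/analyses) will exclude/censor data for patients (as applicable) receiving crossover treatment". It deals with crossover after the November 17, 2017 unblinding and not with the selection of responders.

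Section 1.2 describes the natural history: "DT/DF can have a waxing and waning pattern and on rare occasions exhibit spontaneous remission".

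**The concern.** A patient who never responds has no start date, so the log-rank test can include only responders, although the section does not use that phrase. Response happens after randomisation, and sorafenib is expected to cause it. Placebo responders would be patients whose tumors shrink untreated. Sorafenib responders would be patients of that kind plus those who respond only because of the drug. Randomisation balances the full arms but not these two subgroups, so a difference in duration can arise from who is in each group even if treatment changes nobody's duration.

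The risk is that a p-value printed beside duration of response is read as a treatment effect. A non-significant result could equally be misread as evidence that responses last equally long in both arms.

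**Working it through.** The plan states no figure for duration of response, so there is none to reproduce.

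**Inputs from the documents**
- 50 sorafenib and 25 placebo patients (Section 15.1.1).
- 25% response in the retrospective sorafenib series, 6 of 24, all partial (RECIST paragraph of Section 1.10).

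**Assumptions, because the documents give no values**
- Placebo (spontaneous) response rate p of 4%, 8% or 12%, the same underlying rate in both arms. Sorafenib brings the total to 25%.
- Exponential durations, with a median of 15 months for responses caused by sorafenib and a median m of 6, 15 or 36 months for spontaneous responses. Treatment does not alter the duration of a spontaneous response.
- Two-sided 5% for the log-rank test.

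**Step 1. Responders.** Sorafenib: 50 × 0.25 = 12.5. Placebo: 25p = 1, 2 or 3.

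**Step 2. Chance that the test cannot be run.** P(no placebo responder) = (1 − p)^25, which is 0.96^25 = 36%, 0.92^25 = 12% and 0.88^25 = 4%.

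**Step 3. Best-case power.** Suppose every responder is seen to progress and the true hazard ratio is 0.40. With a sorafenib and b placebo events, power = Φ(|ln 0.40| × √(ab/(a + b)) − 1.96), where |ln 0.40| = 0.916.

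| p | a, b | ab/(a + b) | Power |
|---|---|---|---|
| 4% | 12.5, 1 | 0.926 | 14% |
| 8% | 12.5, 2 | 1.724 | 22% |
| 12% | 12.5, 3 | 2.419 | 30% |

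Censored responses lower these values.

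**Step 4. Direction of the bias.** Among sorafenib responders the share of spontaneous ones is w = p/0.25. The median duration t solves w·2^(−t/m) + (1 − w)·2^(−t/15) = 0.5. On placebo the median is m.

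| p | w | m = 6: sorafenib vs placebo | m = 15 | m = 36 |
|---|---|---|---|---|
| 4% | 0.16 | 12.9 vs 6 | 15 vs 15 | 16.9 vs 36 |
| 8% | 0.32 | 11.0 vs 6 | 15 vs 15 | 19.3 vs 36 |
| 12% | 0.48 | 9.4 vs 6 | 15 vs 15 | 22.2 vs 36 |

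In every cell sorafenib adds responses and changes no existing one. Responders-only duration favours sorafenib, shows nothing or favours placebo according to m alone. Varying p changes the size but not the sign.

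**Step 5. The same scenarios in all randomised patients (p = 8%).** Proportion of each arm still in response 12 months after response onset, non-responders counted as not in response:
- m = 36: sorafenib 0.08 × 2^(−12/36) + 0.17 × 2^(−12/15) = 0.0635 + 0.0976 = 16%; placebo 0.0635 = 6%.
- m = 6: sorafenib 0.08 × 0.25 + 0.0976 = 12%; placebo 0.08 × 0.25 = 2%.

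With everyone in the denominator, the comparison credits sorafenib with its added responses under either assumption.

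**The case against.** A reader might infer that the planned test is likely to declare sorafenib responses shorter. The documents do not support that. The inference needs spontaneous responses that outlast drug responses, and no duration for them is given. A waxing and waning course fits short spontaneous responses at least as well, and Step 4 shows the sign turning when the spontaneous median is 6 months. Even in the 36-month scenario, simulation at 50 versus 25 patients gives a significant result against sorafenib in only about 1% to 2% of trials. That run assumes about 26 months of observation after response, from the 3-year maximum follow-up in Section 15.1.3 less the 10-month median time to partial response in Section 1.10. The estimate pointed against sorafenib in about 63% of those trials, but the p-value seldom says so.

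The analysis is also minor. Section 2.2.3 lists tumor response rates and survival as objectives and does not name duration of response. The test has no part in the decision rule of Section 15.1.1. Best objective status and PFS are already compared by randomised arm. All of this stands and limits the weight of the point, but none of it turns the responders-only test into a valid treatment comparison.

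Two practical objections also stand. Bare medians by arm would invite the same misreading as the p-value unless they are labelled. And the current text follows the November 2017 unblinding, so removing a prespecified test is a post-unblinding change to the analysis.

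**Conclusion.** The defect follows from the definition of the endpoint and needs no assumption beyond an effect of treatment on response. The log-rank test on duration of response is not protected by randomisation, and the Section 15.2 note and the separate Cochran-Mantel-Haenszel test do not repair it. The direction of the bias cannot be stated from the documents. A spontaneous median of 36 months gives 19 versus 36 months and one of 6 months gives 11 versus 6, both at an assumed 8% spontaneous rate. At this trial's size the likeliest outcome is an uninformative test, with best-case power of 14% to 30% and a 4% to 36% chance of no placebo responder, over assumed placebo rates of 4% to 12%. The claim that the p-value will point against the better arm goes beyond the evidence. The consequence is confined to a secondary endpoint.

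**What to change.** In Section 15.2.4:

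- Remove the between-arm log-rank test of duration of response.
- Report duration by arm descriptively, with the number of responders and the Kaplan-Meier median and confidence interval. Label it as conditional on response and not a randomised comparison.
- For any between-arm statement, compare the probability of being in response over time, or mean time in response, in all randomised patients, with non-responders counted as zero.

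Record this as a change made after the November 2017 unblinding, with the reason. Make the same change in Section 15.3.2, where duration of pain palliation is defined only for patients with confirmed palliation and is also compared by log-rank test, there as an exploratory analysis.

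The cost is a short SAP edit with a documented rationale and the loss of one secondary p-value that could not be interpreted. No new data are needed.

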### 15.3 Correlative Companion Study Endpoints

#### 15.3.1 Statistical design- Imaging study

About 50% (38 patients) are expected to have extra-abdominal disease and be evaluated by MRI. Percent change in tumor size by RECIST and percent changes in MRI T2 signal will be calculated at baseline and at response evaluation every 8 weeks. Best RECIST response (ordinal variable) and percent T2 signal change (continuous) will be correlated by Spearman's rho. Careful attention will be paid to patients having received sorafenib after PD on the placebo arm, which may involve censoring or adjusting the patient baseline at the initiation of sorafenib. The percent changes in MRI T2 signal from Week 8 to subsequent imaging will be compared between groups with >30% pain palliation using t-test or a nonparametric alternative (e.g., Wilcoxon rank-sum test). Data, analyses, and censoring will also follow the note described in [Section 15.2](#).

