### 2.3 Correlative Companion Study Objectives

- 2.3.1 To evaluate changes in MRI T2 to predict (or correlate) with a biological effect such as tumor growth (by RECIST v1.1), and pain palliation.
- 2.3.2 The mechanism of action of sorafenib in DT/DF remains unknown. In patients consenting to undergo the paired tumor biopsies (A091105-ST1), treatment induced changes will be quantified by histology, gene expression profiling, proteomic changes and selected interrogation of key pathways by Western blot and RT-PCR.
- 2.3.3 To collect archival tissue, baseline (tumor, blood) and day 8 (tumor, blood) specimens for basic science research (A091105-ST1).
- 2.3.4 To assess patient-reported adverse events and quality of life (QOL) as measured by the PRO-CTCAE and the single-item overall LASA (A091105-HO1).
- 2.3.5 To assess pain palliation measured by the “worst pain” item of the Brief Pain Inventory Short Form (A091105-HO1).

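### The imaging analysis correlates T2 change only with the best RECIST category, although percent change in tumor size is already calculated; adding a continuous correlation would recover power at almost no cost.

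*Combined protocol and SAP*

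**What the plan says.** Section 15.3.1 sets the sample: "About 50% (38 patients) are expected to have extra-abdominal disease and be evaluated by MRI". It then derives two continuous measures on an 8-week schedule: "Percent change in tumor size by RECIST and percent changes in MRI T2 signal will be calculated at baseline and at response evaluation". The stated association with tumor size, a Spearman rank correlation, uses the response category instead: "Best RECIST response (ordinal variable) and percent T2 signal change (continuous) will be correlated by". The section also compares T2 change by pain palliation. It assigns the continuous size change to no analysis, and gives no alpha, power or target correlation.

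The aim is worded in two ways. Objective 2.3.1 speaks of "a biological effect such as tumor growth (by RECIST v1.1") and of pain palliation. Section 10.1.1, which calls the work exploratory, names RECIST response and pain palliation. Section 1.10 has two hypotheses: that T2 signal predicts RECIST response early, and that it predicts clinical benefit in patients with stable disease.

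The only category mix in the documents is the retrospective series in Section 1.10. It had no complete responses and "6/24 partial responses (25%), 17/24 (70%) with stable disease and 1 patient with progressive disease". Seven patients in that series had a 10–29% decrease.

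**The concern.** Section 13.4.3 requires at least a 30% decrease for a partial response, so a patient with a 29% shrinkage and one with no change both count as stable disease. In a disease where most patients stay in that category, the ordinal variable holds little of the size information the trial has already measured. The objective on tumor growth is graded, but its only test is not.

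With at most about 38 patients, the ties make it more likely that a real association is missed. They also lower the correlation that would be reported.

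**Working it through.** **Sample size.** Section 15.1.1 states: "We will randomize a total of 75 patients (25-placebo, 50-sorafenib"). Half of 75 is 37.5, which rounds to the plan's 38. There is no stated power figure to reproduce.

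**How much the ties matter, by arithmetic.** The shares are 6/24 = 25.0% PR, 17/24 = 70.8% SD and 1/24 = 4.2% PD.
- Tied pairs in the series: (6×5 + 17×16)/2 = 151, out of 24×23/2 = 276 pairs, or 55%.
- With mid-ranks, the largest Spearman rho a categorised variable can reach against a continuous one is about √(1 − Σp³). Here Σp³ = 0.0156 + 0.3553 + 0.0001 = 0.371, and √0.629 = 0.79. Even a perfect monotone relation would be reported as about 0.79.

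**Power, by simulation.** T2 change and size change were drawn as bivariate normal with correlation rho. Size change was cut at the shares above. Spearman's rho with mid-ranks was tested two-sided at 0.05 by the t approximation on n − 2 degrees of freedom, with 10,000 runs per cell. Rho, the normal model and alpha are assumptions.

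Results for n = 38 with the Section 1.10 mix:

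| rho | Category | Continuous | Loss (points) |
|---|---|---|---|
| 0.3 | 30% | 41% | 10.8 |
| 0.4 | 50% | 67% | 17.2 |
| 0.5 | 71% | 87% | 15.8 |
| 0.6 | 87% | 97% | 9.9 |
| 0.7 | 96% | 99.7% | 3.4 |

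At rho 0.5 the mean Spearman estimate falls from 0.47 to 0.39.

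**Sensitivity to the mix.** The retrospective mix has 4% progression, but the trial includes a placebo arm. Section 15.1.1 assumes median PFS of 6 and 15 months. If PFS is exponential (an assumption), the share progressed by the first 8-week scan (1.84 months) is:
- placebo: 1 − 2^(−1.84/6) = 19.1%
- sorafenib: 1 − 2^(−1.84/15) = 8.2%
- weighted 2:1: (2×8.2 + 19.1)/3 = 11.8%

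Mixes with more progression at n = 38 (PR/SD/PD), rho 0.3 to 0.6:

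| Mix | Loss (points) |
|---|---|
| 33/55/12 | about 3 to 9 |
| 20/60/20 | 4 to 9 |
| 25/63/12 | about 5 to 10 |
| 15/70/15 | 7 to 12 |
| 17/71/12 | about 7 to 13 |

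For the last mix, a 40,000-run check gave 8.9, 13.3, 12.9 and 7.3 points at rho 0.3, 0.4, 0.5 and 0.6, with a peak of 13.9 at 0.45. Another run put the top at 15. At rho 0.7, the mixes with more progression lose about 1 to 2 points.

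**Other directions.** A more concentrated 10/80/10 mix loses 13 to 21 points. If only sorafenib-arm patients are analysed, n is about 50/2 = 25, and the retrospective mix loses 8 to 18.5 points.

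**The case against.** The strongest defence is that the category matches a stated question. Section 1.10 (first hypothesis) and Section 10.1.1 both name RECIST response, and best RECIST response tests that directly. This stands. A reader might infer that the category is the wrong endpoint and should be replaced, but the documents do not support that. Section 1.10 reports T2 changes up to six months before a RECIST response, so a correlation confined to one imaging window could not test early prediction.

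A reader might also infer that the category fails the stable-disease hypothesis because it cannot separate patients with stable disease. That hypothesis concerns clinical benefit: Section 1.10 describes symptomatic improvement without a RECIST response. Finer size measurement within stable disease would not test it, and the pain-palliation comparison in Section 15.3.1 addresses it at least in part.

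The size of the loss is also conditional. The 70% comes from 24 sorafenib-treated patients at all sites; 12 of the full 26 had abdominal or pelvic tumors. The 38 are extra-abdominal and may include placebo patients, and Section 1.10 reports that response differed by site. This stands, and is why a range of mixes is shown.

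Finally, Spearman's rho with mid-ranks is valid for tied data, the study is exploratory, and the size data remain available. All true. None of it explains why the continuous measure is calculated and then given no analysis.

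**Conclusion.** The concern holds as one of efficiency. At n = 38, under two-sided 0.05 and a bivariate normal correlation of 0.3 to 0.6, correlating T2 change only with best RECIST category costs about 10 to 17 points of power if the mix matches Section 1.10. It costs about 3 to 13 points with mixes that have more progression. At a correlation of 0.7 the cost is about 1 to 3 points across these mixes. Alpha and the correlation are assumptions, and the mix is borrowed from a small series.

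A reader might take 10 to 17 points as the expected loss in this trial. The documents do not support that as an unconditional figure, because they give neither the correlation nor the category mix for these 38 patients. Nor is any stated figure wrong: Section 15.3.1 claims no power, and no primary or secondary trial conclusion depends on this analysis.

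**What to change.** Add one sentence to Section 15.3.1 specifying a Spearman correlation of percent T2 change with continuous percent change in the sum of diameters. Use best percent change from baseline, and the change at matching scans. Label it the analysis of tumor growth under objective 2.3.1, with the crossover and censoring handling the section already describes.

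Keep the planned Spearman correlation with best RECIST category for the RECIST-response hypothesis.

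This needs no new scans, patients or measurements. The only cost is one more exploratory correlation to report.
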